4.3 Intervention

Nature-based therapy (NBT) consists of the components green exercise/hiking and nature-based mindfulness training.

The hikes are designed to accommodate individuals with varying levels of fitness. Each hike lasts between 1.5 and 2 hours. Participants will traverse distances between 3 and 6 kilometers and ascend to elevations of up to 300 meters on the Salzburg city mountains. A heart rate monitor (wristwatch) will be provided to each participant, which will be calibrated to their specific gender, age, height, and weight. This monitor will be used throughout the intervention. It is recommended that participants complete the hikes within the range of 60-70% of their maximum heart rate (Steele et al., 2021). Additionally, it is advised that training be conducted at a medium level of exertion on the Borg scale (12-16) (Borg, 1982; Löllgen, 2004). A guided group is limited to a maximum of 15 participants and is accompanied by a hiking guide and a mindfulness trainer.

Mindfulness training is based on concentrative movement therapy (Stolze & Badura-MacLean, 2002), a body psychotherapy method that combines physical movements and concentration to promote awareness and mindfulness of one's own body. The objectives of this form of mindfulness training are threefold: firstly, to enhance body awareness through targeted movement exercises; secondly, to reduce stress and promote general well-being; and thirdly, to cultivate mindfulness by training individuals to focus their attention on the present moment.

Intervention group (Nature group) :

Week 1 (day 0 - day 7): Onboarding

- a. 3 x 1,5-2h Green Exercise (guided hikes on the Salzburg city mountains,
 3-6 km each, 100-300 hm, max. 15 people per group)
- b. Within these hikes, participants will receive 20 minutes of nature-based mindfulness training under the guidance of a therapist in a pre-selected restorative and safe location. It is important to note that participants will learn mindfulness training during the process so that they can continue to practice it independently.
- c. It is required that all participants engage in the guided hikes during the initial week of the program.

Week 2 – Week 5 (day 8 – day 35): Integration

- a. 3 x 1,5-2h Green Exercise per week (guided or self-guided hikes (participants can choose) on the Salzburg city mountains, 3-6 km each, 100-300 hm)

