4.5 Study timeline

Participation in the clinical study involves four measurement time points over a period of 180 days:

- **T1 (day 1):** Baseline data assessment directly before the intervention for intervention and control group; data assessment at the premises of the Paracelsus Medical University Salzburg
- **T2 (day 35):** data assessment after the onboarding (week 1) and integration phase (week 2-5) for all study participants of the intervention and control group at the premises of the Paracelsus Medical University Salzburg
- **T3 (day 70):** data assessment for all study participants of the intervention and control group after the first follow-up phase (week 6-10) at the premises of the Paracelsus Medical University Salzburg
- **T4 (Tag 180):** data assessment for all study participants of the intervention and control group after the first follow-up phase (week 6-10) via online questionnaire

[figure not shown]

Figure 1: Study timeline

The present clinical study is planned in two rounds:

- Round 1: from September 2024: intervention group, waiting list control group
- Round 2: ab March 2025: intervention group, waiting list control group

The implementation in two rounds results from the capacities of the study team (hiking guides, therapists).

For ethical reasons, the control group is designed according to the principle of a waiting list control group (Elliott & Brown, 2002). This implies that the individuals in the control group will also have the chance to benefit from the nature-based therapy. The offer will be made to the control group after all measurements have been completed (after t4) in spring and fall 2025.

The allocation of groups is random.

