4.6 Sample size

The calculation of the sample size is based on published study results from the Institute of Ecomedicine. The study investigated the effect of nature-based therapy on individuals with sedentary lifestyles. (Huber et al., 2023; Pichler et al., 2022, ISRCTN43292449 https://doi.org/10.1186/ISRCTN43292449):

- Study type: two-armed randomized controlled clinical trial
- Intervention: nature-based therapy (mindfulness-based forest therapy vs. hiking; Forest vs. Hiking)
- Outcome parameter for sample size calculation: health-related quality of life (SF-12)
- Study population: 50-60 years, sedentary lifestyle, moderate overweight (BMI ≥25–≤30)

The sample size was calculated with a bootstrap simulation (using the software R-GNU, Genal Public License, R Foundation for Computing), applying the F1-LD-F1 model from the nparLD package (Nonparametric Longitudinal Data Analysis) (Noguchi et al., 2012). The initial seed for the variate generator was set at 1 and the re-sampling process was fixed to 1000 repetitions for each sample size. The percentage of significant results was used as an estimator of power.

Regarding clinical studies on lifestyle interventions in overweight individuals, recent literature reports dropout rates ranging from 30% to 50% (Collins et al., 2022; Ruelas et al., 2023).

A drop-out and lost-to-follow-up rate (until T4 = day 180) of 40 % was assumed for the present study, resulting in a sample **size of n=70 per study arm**.

Sample size	Туре	FALSE	TRUE	Power	Comparison
10	nparLD	698	302	0,302	FoHi
20	nparLD	485	515	0,515	FoHi
30	nparLD	316	684	0,684	FoHi
40	nparLD	183	817	0,817	FoHi
50	nparLD	127	873	0,873	FoHi
60	nparLD	58	942	0,942	FoHi
70	nparLD	38	962	0,962	FoHi
80	nparLD	18	982	0,982	FoHi
90	nparLD	11	989	0,989	FoHi
100	nparLD	3	997	0,997	FoHi

Table 1: Sample size calculation based on Huber et al., 2023

FoHi = Forest vs. Hiking

[figure not shown]

Figure 2: Sample size calculation based on Huber et al., 2023

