4.7 Recruitment

The clinical study will recruit a total of 140 participants, with 70 in each study arm. The University Clinic for Internal Medicine I of the Salzburg University Hospital (study center 2) will conduct clinical inclusion, while the Institute for Ecomedicine of the Paracelsus Medical University Salzburg (study center 1) will carry out the intervention.

Study participants can register for the study through the Paracelsus Medical University website (primary source, www.pmu.ac.at/ecomedicine).

A total of 140 study participants are recruited through the following channels:

1) Paracelsus 10,000 data base

People with metabolic syndrome aged between 40 and 65 years will be identified from the database of the Paracelsus 10,000 Study(Frey et al., 2021). A sample of n=500 people, stratified by age and sex, will then be selected from these data and informed by post about the possibility of participating in the study.

2) University clinic for internal medicine I of the Salzburg University Hospital

In addition, recruitment will take place via the outpatient clinics (metabolic, diabetes, obesity) of the University Clinic for Internal Medicine I of the University Hospital Salzburg (head physician: Univ. [name]. [name]; active approach of eligible persons, website, distribution of information material).

3) Resident general practitioners and internists

Information material about the study will be sent to local internists and general practitioners (GPs) in the city of Salzburg and surrounding communities to make eligible patients aware of the opportunity to participate in the study.

The design and content of the digital and analog advertising material are identical.

The communication of the clinical study and the recruitment of study participants will be carried out in compliance with the guidelines for advertising study participation of the Ethics Commission of the Federal State of Salzburg.

An online questionnaire will be used for enrolment and an initial assessment of the inclusion and exclusion criteria. The data collected during registration will be stored on a secure server at the Paracelsus Medical University of Salzburg and will only be used to contact participants and assess their eligibility. The data will be deleted after recruitment is completed.

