6.3 Statistics

All statistical analyses will be performed using the R-GNU software environment (General Public License, R Foundation for Statistical Computing, Vienna, Austria) and SPSS (IBM). Statistical significance will be set at the level of a < 0.05 for all tests. Randomly missing values will be replaced using the standard procedure, last outcome carried forward (LOCF). The statistical analysis will be carried out by a biometrician. The data will be blinded again in order to exclude a possible bias with regard to an expected result.

Statistical analyses will be performed in accordance with the intention-to-treat principles and reporting will adhere to the CONSORT-statement, including CONSORT flow chart (Calvert et al., 2013; CONSORT, 2019).

After a positive vote, the study will be preregistered in the ISRCTN registry (https://www.isrctn.com/).

Check for normal distribution

The Shapiro-Wilk test will be applied to check for normal-distribution. Depending on data distribution, parametric or non-parametric tests will be applied.

Analysis of Baseline values

To analyze possible baseline differences between the two groups, a t-test for unconnected samples is performed for normally distributed variables and a Mann-Whitney Utest for non-normally distributed parameters. Nominally scaled variables are analyzed using the chi-square test. If any baseline variables are significantly different between the groups, secondary analysis will be conducted including these variables to adjust for any residual confounding not prevented by the randomization.

Longitudinal Data analysis

Depending on data distribution, parametric or non-parametric tests will be applied. Participant data will be compared in terms of baseline data, including outcome variables as well as demographics (unpaired Student-T-Test or Wilcoxon-test).

For longitudinal data analysis, analyses of variance (ANOVA) or linear mixed models (LMM) are used for normally distributed data.

For non-normally distributed samples, a non-parametric analysis of variance (e.g. f1.LD.f1) is performed using the nparLD package (Noguchi et al., 2012).

Models will include random effects for temporal and spatial correlations and fixed effects for: (1) intervention group; (2) time effects characterizing changes between pre- and post-intervention; and (3) interaction between the intervention group and the pre- and

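### The Section 6.3 model names neither the hiking group (intervention arm only) nor the round, so any within-group correlation would make the arm-by-time test somewhat anti-conservative

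*Protocol*

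**What the plan says.** **Delivery (Protocol 4.3).** "A guided group is limited to a maximum of 15 participants", each led by a hiking guide and a mindfulness trainer. Guided hikes are compulsory in week 1, a matter of choice in weeks 2 to 5, and not offered in weeks 6 to 10. Controls attend the examinations only.

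**Rounds (Protocol 4.1 and 4.5).** "Round 1: from September 2024: intervention group, waiting list control group"; a second round with both arms starts in March 2025. Controls are examined at the same time as the intervention group. Randomisation (5.1) is stratified by age and gender; round is not mentioned.

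**Model (Protocol 6.3).** "Models will include random effects for temporal and spatial correlations and fixed effects for: (1) intervention group", followed by time and by the arm-by-time interaction, which carries the group contrast. The unit of the random effects is not given. For non-normal data the protocol offers a non-parametric analysis, with f1.LD.f1 as the example.

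**Sample size (Protocol 4.6).** The power table was simulated with the same F1-LD-F1 model for the SF-12, and the section describes no allowance for clustering.

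**The concern.** People who share a guide, a trainer and fellow walkers may change in similar ways. The protocol itself (3.1) expects group activities to build social resilience, so some similarity is part of its reasoning. It would most plausibly show in the SF-12, a primary outcome, and in loneliness and community cohesion. The correlation arises in one arm only, and a model that treats all participants as independent then understates the standard error of the arm contrast.

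Round is a separate matter. The 70 days from T1 to T3 run from September towards winter in one round and from March towards summer in the other. A single time effect is fitted to both, so any seasonal difference in change goes into the residual.

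This goes beyond detail that a protocol leaves to an SAP. Section 6.3 already lists its fixed and random effects, and that list does not match how the intervention is delivered.

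**Working it through.** **Inputs from the protocol**
- Two-sided testing is assumed (the sides are not stated): "Statistical significance will be set at the level of a < 0.05 for all tests".
- "size of n=70 per study arm", with 40% loss assumed: 70 × 0.6 = 42 completers per arm.
- Group cap 15, two rounds.

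**Assumptions not in the protocol**
- Equal rounds: 35 intervention participants each. 35/15 = 2.33, so at least 3 groups per round and 6 in all.
- Group size m: 42/6 = 7 completers, or 70/6 = 11.7 if everyone is analysed. The second case matters because 6.3 prescribes intention-to-treat with last values carried forward.
- Membership is stable over the trial.
- ICC of the change within a hiking group: 0.01, 0.05 or 0.10.

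**Consistency check on Table 1.** No effect size is stated. Taking n as per arm, a standardised effect of 0.633 gives power 0.808 at n = 40 (table 0.817), 0.886 at 50 (0.873) and 0.963 at 70 (0.962); all ten rows agree within 2 percentage points. The effect is solved from the table, so this does not validate it independently. At 42 per arm, power is Φ(0.633 × √(42/2) − 1.96) = 0.827.

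**Clustering in one arm**
- Design effect in the intervention arm: DE = 1 + (m − 1) × ICC.
- Variance ratio of the arm contrast: VR = (DE + 1)/2. True SE / naive SE = √VR.
- Type I error = 2 × [1 − Φ(1.96/√VR)].

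| m | ICC | DE | VR | √VR | Type I error |
|---|---|---|---|---|---|
| 7 | 0.01 | 1.06 | 1.03 | 1.015 | 0.0535 |
| 7 | 0.05 | 1.30 | 1.15 | 1.072 | 0.0676 |
| 7 | 0.10 | 1.60 | 1.30 | 1.140 | 0.0856 |
| 11.7 | 0.01 | 1.107 | 1.053 | 1.026 | 0.0562 |
| 11.7 | 0.05 | 1.533 | 1.267 | 1.125 | 0.0816 |
| 11.7 | 0.10 | 2.067 | 1.533 | 1.238 | 0.1135 |

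Simulating an ordinary t-test with six groups in one arm (40,000 runs per setting) gave 0.054, 0.067 and 0.086 for 42 per arm, and 0.055, 0.080 and 0.114 for 70 per arm. With exactly 12 per group the last row becomes 11.5%.

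Power with the correct SE at 42 per arm, Φ(0.633 × √21/√VR − 1.96), is 0.815, 0.772 and 0.720 for the three ICCs, against 0.827 without clustering. These use a normal critical value; few degrees of freedom would lower them further.

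**Round.** Let R² be the share of variance in the analysed change explained by round. Unadjusted SE / adjusted SE = 1/√(1 − R²). For R² of 1%, 5% and 10% this is 1.005, 1.026 and 1.054; adjusting raises power at 42 per arm from 0.827 to 0.830, 0.845 and 0.864. For R² of 5% and 10%, simulated type I error of the unadjusted test (20,000 runs each) was 0.049 and 0.048 with round unbalanced across arms, and 0.046 and 0.039 with arms balanced within round. Nothing is inflated.

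**Which group term is needed.** T1 is taken directly before the intervention, so hiking-group effects arise in the change from T1. A random intercept for group that is constant over time appears in both the T1 and the later value of the same person and largely cancels from the arm-by-time contrast. Only a group effect on post-baseline change reaches the SE at issue.

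**The case against.** The protocol does plan random effects, and defining their units, the degrees of freedom and covariates is often left to an SAP, which may exist. A reader might infer that the mixed model ignores clustering altogether. The text does not support that: the unit is undefined, which is a different fault. The point about f1.LD.f1 is firmer, since that design has one between-subject and one within-subject factor. Even so, it is only an example and applies only to non-normal data.

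Stable groups are not stated either. The protocol caps group size but does not say that membership is fixed or that each group keeps its guide and trainer. Of 30 planned sessions (3 × 10 weeks), 3 must be guided, 12 may be guided and 15 are self-guided, and T3 falls five weeks after the last guided hike. The ICC may well be small, and at 0.01 the inflation is slight. This objection stands and limits the size of the finding.

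A reader might also infer that season biases the comparison of arms. It does not: both arms run in each round and are examined at the same time. A constant difference in level between rounds also drops out of within-person change. No passage shows that the SF-12 or the Allostatic Load Index changes differently by season, so round is a precision covariate and its omission is not an error of inference.

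What remains is that 6.3 lists its model terms and leaves out the one source of dependence that the delivery of the intervention creates.

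**Conclusion.** The point holds in a limited form. As written, 6.3 does not define its random-effect units and names neither hiking group nor round. If change is correlated within hiking groups, the arm-by-time test is anti-conservative, with type I error between about 5.3% and 8.6% at 7 completers per group, or 5.6% and 11.3% with all 70 analysed. Those figures depend on an assumed ICC of 0.01 to 0.10, six groups and stable membership; none of these is in the protocol, and the limited guided contact points towards the lower end. The upper figures should not be read as the trial's expected error rate. Leaving out round costs about 0.5% to 5% in SE if round explains 1% to 10% of the variance in change, and nothing in validity. This is a worthwhile, inexpensive improvement; the design itself is not called into question.

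**What to change.** In Protocol 6.3:
- Replace the temporal and spatial wording with a participant random effect plus a hiking-group random effect on post-baseline change (group-by-time, intervention arm only, controls as singletons), with small-sample degrees of freedom such as Kenward-Roger or Satterthwaite.
- Add round and round-by-time as fixed effects, coded so that arm-by-time remains the effect averaged over rounds.
- For non-normal data, name an analysis that can carry these terms.

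In data collection, record the week 1 hiking-group number in REDCap. The listed MyCap items capture individual or group setting but not which group, and this may be hard to reconstruct later.

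The cost is wording and one data field. About six groups leave few degrees of freedom for the group variance, so intervals may be somewhat wider. If membership mixes in weeks 2 to 5, the week 1 group only approximates the clustering, and the report should say so.

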4.4 Outcome parameters

4.4.1 Primary endpoints

The primary endpoint of the present clinical study is the effect of the intervention on biopsychosocial resilience (White et al., 2023), quantified in relation to MetS by recording following parameters. (see also Figure 1 for definition of time points) :

I. Primary endpoints t1-t3

1) Health-related quality of life (SF-12) (Weinhardt & Richter, 2013)

Health-related quality of life is measured by the German version of the Short Form Health Survey SF-12. The SF-12 measures health-related quality of life in two summary scales (physical health (PH) and mental health (MH)) (Weinhardt & Richter, 2013). This means that the SF-12 can map the two summary scales of the SF-36. However, the SF-12 consists of only 12 items and can therefore be completed in less time (Y. Lin et al., 2020; Ware & Gandek, 1998; Wee et al., 2008). The total scale ranges from 0 to 100 points, with higher scores reflecting better quality of life (Ware & Gandek, 1998).

The threshold for a clinically significant change in QoL should always be considered in relation to the change in other parameters (e.g. ALI) (Ware et al., 1995). In general, a change of 2.5-5.0 points on a summary scale is considered clinically relevant (Fan et al., 2004).

In the present study, a change in the SF-12 total score of 2.5 points or more is therefore defined as a clinically relevant change.

2) Allostatic Load

- a. Allostatic Load Index 1 (derived from: (Adams-Campbell et al., 2021; McCrory et al., 2023):
 - Dehydroepiandrosterone sulfate (DHEA-S)
 - Heart rate variability (HRV)
 - Systolic and diastolic blood pressure
 - Resting heart rate
 - Peak Expiratory Flow (PEF)
 - HDL Cholesterol
 - LDL Cholesterol
 - Triglycerides
 - HbA1C
 - Waist-hip ratio
 - C-reactive protein (CRP)
 - Interleukin-6
 - TNF-alpha
- b. Allostatic Load Index 2 (experimental, non-invasive):
 - Dehydroepiandrosterone sulfate (DHEA-S) from saliva
 - Heart rate variability (HRV)
 - Systolic and diastolic blood pressure
 - Resting heart rate
 - Peak Expiratory Flow (PEF)
 - Waist-hip ratio
 - C-reactive protein (CRP) from saliva

A clinically relevant change in the Allostatic Load Index (ALI) is defined as a reduction in the ALI value that reflects a significant improvement in physiological markers associated with chronic stress and metabolic dysfunction. To be considered clinically relevant, a change should indicate a significant improvement in the above biomarkers, leading to improved overall health and reduced risk of metabolic and cardiovascular disease. In clinical trials, a reduction in ALI of approximately 0.5 to 1.0 standard deviations is often used as a threshold for clinical relevance. This range indicates a significant reduction in physiological stress, which can have a significant impact on overall health and the risk profile for complications associated with metabolic syndrome (Osei et al., 2022). In the present study, a reduction in ALI of 0.5 standard deviations or more is therefore defined as a clinically relevant change.

II. Primary endpoints – Perception of the intervention and short-term effects (t1-t4)

The evaluation of individual nature-based interventions is conducted using the MyCap mobile app (Harris et al., 2022). Participants are asked to complete the following questionnaires for each session:

- 1) Nature connection at the nature exposition site
- 2) Individual or group setting
- 3) Provide details on the mode of transportation used to reach the intervention site, such as public transport, car, or bicycle.
- 4) Perceived Exertion during physical activity via Borg Scale (Löllgen, 2004)
- 5) Surrounding photo (no identifiable persons!)
- 6) Affective states:
 - a. German version of the Scale of Positive and Negative Experience (SPANE) (Diener et al., 2009)
 - b. German short version of the Perceived Restorativeness Scale (PRS), (Pasini et al., 2014)
- 7) Ecologic aspects
 - a. Landscape
 - b. Environmental attitudes
 - c. Crowding
- 8) Overall satisfaction with NbT session

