post-intervention temporal effects, representing the group contrast. This determines whether or not the intervention has an effect. If any baseline variables are significantly different between the groups, secondary analysis will be conducted including these variables to adjust for any residual confounding not prevented by the randomization.

Multiple testing:

We will adjust for multiple testing, e.g., Benjamini-Hochberg or Holm-Bonferroni.

7 Methods: Data monitoring

The responsibility for the complete and correct data collection and documentation as well as the safe storage of the data in the context of the clinical study lies with the staff of the Paracelsus Medical University and the University Clinic for Internal Medicine I of the University Hospital Salzburg.

Data will only be shared with the RESONATE Lead Partner in an ID-encrypted form and in accordance with the RESONATE Data Management Plan (see chapter 6.2 Data management).

Data collection and storage is implemented in such a way as to minimize the possibility of inaccurate, erroneous and/or incomplete data entry. Entries and corrections can only be made by authorized persons. All entries and corrections are dated, documented and traceable or recoverable.

Internal audits shall be conducted at least three times: (1) prior to the start of the clinical trial, (2) during the conduct of the clinical trial and (3) after the completion of the clinical trial. The following activities are planned as part of the internal audits:

- Verification that the trial site meets the requirements of the clinical trial, e.g. requirements for the trial population, equipment, storage of trial materials.
- Comparison of source data
- Verification of proper and safe storage of samples

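### The 2.5-point relevance threshold is taken from an SF-12 summary scale but applied to an SF-12 total score that is never constructed, and the protocol does not say which SF-12 score is primary

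*Protocol*

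**What the plan says.** Section 4.4.1 lists health-related quality of life (SF-12) as the first primary endpoint for t1 to t3. Four statements there bear on the score:

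- On structure: "The SF-12 measures health-related quality of life in two summary scales", namely physical and mental health.
- On range: "The total scale ranges from 0 to 100 points, with higher scores reflecting better quality of life".
- On relevance in general: "In general, a change of 2.5-5.0 points on a summary scale is considered clinically relevant".
- On relevance in this trial: "In the present study, a change in the SF-12 total score of 2.5 points or more is therefore defined as a clinically relevant change".

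The other sections name no score. Section 3.2 gives the primary outcome as quality of life. Section 4.6 gives the outcome behind the sample size as health-related quality of life by SF-12. Section 6.3 says "Statistical significance will be set at the level of a < 0.05 for all tests" and "We will adjust for multiple testing, e.g., Benjamini-Hochberg or Holm-Bonferroni", and does not say whether the SF-12 contributes one test or two.

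**The concern.** The word *therefore* in the threshold sentence carries a figure from one score to another. The cited range belongs to a single summary scale, whereas the trial's threshold is placed on a total. The protocol gives no formula for that total, so the threshold has no defined meaning on it.

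The larger problem is that the primary variable is not identified. Physical, mental and combined scores are all compatible with the text and can give different answers. The intervention combines hiking with mindfulness training, so its effects on physical and mental health need not agree. If the choice is made after results are known, the nominal 5% level no longer describes the error rate. The size of the multiplicity family also depends on the answer.

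**Working it through.** **1. The plan's own figure.** The bootstrap in section 4.6 cannot be rerun, because the earlier trial's data are not in the protocol. The dropout step can be checked, reading the table's sample sizes as per arm:

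- Completers: 70 × (1 − 0.40) = 42 per arm.
- In reverse: 42 / 0.60 = 70, while 40 / 0.60 = 66.7, that is 67. The 70 therefore fits a requirement of about 40 per arm, rounded up.
- Power at 42, interpolated between the rows for 40 (0.817) and 50 (0.873): 0.817 + 0.2 × (0.873 − 0.817) = 0.828.

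The 2.5 points does not enter this calculation, and nothing here overturns the 70 per arm.

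**2. Does the threshold carry over to an average?** Let the changes on the physical and mental scales be P and M, and let the total be (P + M)/2.

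| P | M | Average | Reaches 2.5? | Relevant on a summary scale by the cited criterion? |
|---|---|---|---|---|
| 2.5 | 2.5 | 2.5 | yes | yes, both |
| 2.5 | 0 | 1.25 | no | yes, physical |
| 0 | 2.5 | 1.25 | no | yes, mental |

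The two rules agree when both scales move together and disagree when only one moves.

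**3. The same 2.5 points in SD units.** This is an illustration. An SD of 10 per summary scale and a correlation r of 0 to 0.5 between scales are assumptions, since the protocol gives neither.

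- One summary scale: 2.5 / 10 = 0.25 SD.
- Average of two: its SD is 10 × √((1 + r)/2), which is 7.07 at r = 0 and 8.66 at r = 0.5. So 2.5 points is 0.35 SD and 0.29 SD respectively.

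**4. Error rate if the score is chosen after the results.** Assume no true effect, normal test statistics, equal variances, an equal-weight total and two-sided 0.05 for each score. The total is a function of the two scales, and its correlation with each is √((1 + r)/2), at least 0.71 over this range. Simulating the chance that at least one of the three is significant gives:

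- r = 0: about 11.5%
- r = 0.5: about 9.7%

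**5. Power if both scales are primary at 0.025 each.** Normal approximation, same effect on each scale, 42 completers per arm, and the other primary outcomes left aside:

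- Signal implied by power 0.828 at two-sided 0.05: 1.960 + 0.947 = 2.907.
- Critical value at two-sided 0.025: 2.241.
- Power per scale: Φ(2.907 − 2.241) = Φ(0.666) = 0.75.

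**The case against.** The best defence is that total score is loose wording for a summary score, and that the 0 to 100 range describes the full span of each scale. On that reading the 2.5 points sits on the right kind of score and no composite is intended. This is plausible, but it still leaves open whether the physical score, the mental score or both is primary.

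Four stronger readings might be inferred, and the documents do not support them:

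- **That 2.5 points is the trial's success criterion.** Section 4.4.1 calls it a clinically relevant change. Section 6.3 judges the effect by the interaction of group and time at 0.05. The threshold governs interpretation, not the test decision.
- **That the total is a plain sum, so 1.25 points on each scale would suffice.** Two scales of 0 to 100 each would sum to 0 to 200, which does not fit the stated range.
- **That the error rate could reach 1 − 0.95³ = 14%.** That needs three independent tests, and a total cannot be independent of its own components.
- **That the outcome cannot be computed.** Several scores can be computed. The protocol does not say which one counts.

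Two safeguards also deserve credit. Section 6.3 promises adjustment for multiple testing, and sections 5.2 and 6.3 blind the analysing biometrician to allocation. Both limit selective choice in part. Neither names the variable, and an adjustment covers only the tests that are counted.

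**Conclusion.** The point holds as an inconsistency within section 4.4.1 together with an unnamed primary variable. It is not a detail that a protocol may simply leave to an analysis plan, because the protocol fixes a threshold and fixes it on a score other than the one its own citation supports.

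If the total is an average, a change the protocol's criterion calls relevant on one scale registers at half the threshold. A free choice among the three scores would roughly double the nominal 5%, to between 9.7% and 11.5%. That range rests on an equal-weight total and assumed correlations of 0.5 to 0. The unnamed primary variable is the weightier part; the threshold mismatch alone would mainly affect how results are described.

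**What to change.** Before any outcome data are seen:

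1. In section 4.4.1, replace the total score by named summary scores. Either make one primary and the other secondary, or make both primary and count both in the multiplicity family.
2. Apply the 2.5-point relevance threshold to each named summary score.
3. In section 4.6, state which SF-12 score was simulated, so that the power table refers to the endpoint being tested.
4. In section 6.3, count the SF-12 tests in line with the choice made under item 1.

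Defining a total and justifying a separate threshold for it would also remove the contradiction, but it needs support that the protocol does not now cite.

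**Cost.** These are wording changes. One primary scale loses no power, provided it is the score simulated in section 4.6. With both primary at 0.025 each, power per scale falls from about 0.83 to about 0.75 at 42 completers per arm, under the approximation shown.
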